9.1. Point of Enrollment

A subject is considered enrolled in the study when the subject or the subject's legally authorized representative signs an ICF approved by the IEC. No study-specific tests, procedures, etc. can take place until the ICF is signed. A subject who is determined to not

meet study specific clinical eligibility criteria after signing consent will be considered a screen failure (see **Table 9.4-1**) and will not count towards the enrollment ceiling.

9.2. *Withdrawal*

All subjects enrolled in the clinical study (including those withdrawn from the clinical study) shall be accounted for and documented. If a subject withdraws from the clinical investigation the reason(s) shall be reported. Reasons for withdrawal include but are not limited to physician discretion, subject choice to withdraw consent, or death. Reasons for study exit will be captured in the secure electronic data capture (EDC) system. If such withdrawal is due to problems related to device safety or performance, the investigator shall ask for the subject's permission to follow his/her status/condition outside of the clinical study.

While all efforts will be made to minimize attrition, subjects may withdraw from the study at any time, with or without reason, and without prejudice to further treatment. Withdrawn subjects will not undergo any additional study follow-up, nor will they be replaced. The investigator may discontinue a subject from participation in the study if the investigator feels that the subject can no longer fully comply with the requirements of the study or if any of the study procedures are deemed potentially harmful to the subject. Data that have already been collected on withdrawn subjects will be retained and may be used for analysis unless local regulations apply. No new data will be collected after subject withdrawal.

All applicable case report forms up to the point of subject withdrawal and an "End of Study" form for the subject must be completed. If the withdrawal is due to investigator discretion, the investigator should follow-up with the subject per standard of care.

9.3. *Lost to Follow-Up*

All enrolled subjects will be followed for up to 12 months post-procedure.

A subject will be considered lost to follow-up if he or she fails to be available for 2 consecutive scheduled visits without due cause and is unable to be contacted by study center staff. The following actions will be taken if a subject fails to be available for a required study visit.

- The center will attempt to contact the subject and reschedule the missed visit and counsel the subject on the importance of maintaining the assigned visit schedule and ascertain if the subject wishes to and/or should continue in the study.
- Before a subject is deemed lost to follow-up, the investigator or designee will make every effort to regain contact with the subject (where possible, 3 telephone calls and, if necessary, a certified letter to the subject's last known mailing address or local equivalent methods). These contact attempts will be documented in the subject's medical record or study file.
- Should the subject continue to be unreachable, he or she will be considered to have withdrawn from the study with a primary reason of lost to follow-up.

9.4. *Subject Status and Classification*

Table 9.4-1 describes subject status/classification and associated forms.

Table 9.4-1: Subject Status and Classification

Classification	Description
Screen Failure	
A subject who signs an ICF but does not meet clinical eligibility criteria is considered a screen failure. Screen failure subjects do not count towards the enrollment ceiling and will not be used for the primary analyses. Screen failure subjects should exit from the study immediately upon determining ineligibility. The original signed ICF must be maintained in the center's subject file and the following forms must be completed for all information collected prior to determining the subject's ineligibility.
 
• Baseline forms such as, but not limited to, ICF, baseline information and other related forms• Adverse Event form(s) for any reportable event, as defined in Section 18, for any adverse event that occurs after signing the ICF, up to the point of subject exit
Attempt	
A subject who signs an ICF, meets eligibility criteria, and has had a WATCHMAN Access Sheath inserted to implant the device, but eventually does not receive a WATCHMAN FLX Pro device will be classified as "Attempt." Attempt subjects will be followed for 12 months from the time of the implant attempt and adverse events will be collected. Attempt subjects count towards the enrolment ceiling and will be used for analyses of the endpoints. The original signed ICF must be maintained in the center's study file and the following forms must be completed.
 
• eCRFs in the Baseline and Implant folders• First Follow-up Visit Form(s), except LAA imaging• Adverse Event forms and/or Device Deficiency forms for any reportable adverse event that occurs after signing the ICF• End of Study form for withdrawal 
The date of withdrawal should be indicated in the End of Study form as the point of subject withdrawal.

Implant	
A subject who is successfully implanted with the WATCHMAN FLX Pro device will be classified as "Implant." Successfully implanted subjects are those defined as having device success, where the device has been deployed and implanted in the correct position. These subjects are followed in accordance with the follow-up schedule and data will be included in all study analyses. All applicable case report forms per the protocol must be completed. The original signed ICF and any relevant documentation must be maintained in the center's study file.

Abbreviations: eCRF=electronic case report form; ICF=Informed Consent Form; LAA=left atrial appendage

9.5. *End-of-Study Definition*

This clinical study will be considered completed when subjects are no longer being examined or the last subject's last study visit as outlined in the data collection schedule (**Table 10.1-1** below) has occurred. All enrolled subjects will be evaluated clinically post-implant on the procedure day, at predischarge, at 14 days, 45 days, 3 months, and 12 months post implant procedure (preferably all in-person visits; see **Table 10.1-1** for additional information).

At the point of study completion and/or withdrawal, all open adverse events must be assessed by the investigator. These events must be closed or documented as ongoing. Events assessed as related to the device should be followed through resolution if possible, with the consent of the subject provided for collection of this data.

10. Study Methods

10.1. *Data Collection*

This section lists the data needed to fulfill the objectives of this clinical study. Boston Scientific Corporation considers data collected from clinical trial subjects to be personal data (see definitions of different data categories in **Table 25.2-1**) and compliance with privacy and data protection laws and regulations (for example, the General Data Protection Regulation [GDPR]) to be critically important. Data collection for this clinical study has been carefully considered to comply with data privacy laws.

The data collection schedule is provided in **Table 10.1-1** and summarized diagrammatically in

Figure 10.1-1. Additional information, including recommended post-procedure medical therapy, is provided in Section **10.2** through Section **10.10**. It is important that this schedule be maintained as closely as possible for all subjects. Boston Scientific Corporation (BSC) recognizes that subjects may not be able to return for all scheduled visits at precisely the date required, and therefore, a period of time in which each visit is allowed is indicated in **Table 10.1-1**. Required follow-up assessments and visits not completed will be considered missed visits and recorded as protocol deviations. Visits completed outside follow-up windows will be recorded as protocol deviations. Each follow-up visit must be performed by trained study personnel. Data from collected tests and images as well as medical assessments will be recorded in source documentation and captured in the eCRFs.

Table 10.1-1: WATCHMAN FLX Pro CT Study Event Schedule

Assessment	Baseline e	Implant Proced- ure	Predic- harge	14 Day s ^a (\pm 3 Days)	45 Days a (\pm 15 Days)	3 Months a (90 \pm 30 Days)	12 Months ^a (365 \pm 30 Days)
Signed Informed Consent Form (date)	X	—	—	—	—	—	—
Demographics	X	—	—	—	—	—	—
Pregnancy Test ^j	X ^j						
Medical history and inclusion/exclusion criteria	X	—	—	—	—	—	—
Physical assessment	X	—	—	—	X	X	O
Risk factor assessments ^b (HAS-BLED and CHA ₂ DS ₂ -VASC scores)	—	X	—	—	—	—	—
TEE of LAA ^c	X ^c	—	—	X	X	X ^c	O ^d
CT of LAA ^c	X ^c	—	—	X	X	X	O
MRI of LAA ^c	O	—	—	O	O	O	O
Labs – biochemical markers ^f	X	—	—	X	X	X	O
NIHSS Stroke Scale ^g	X	—	—	—	—	—	—
Modified Rankin Scale score ^g	X	—	—	—	—	—	—
Procedural ICE ^h	—	X	—	—	—	—	—
Medications	X	X	X	X	X	X	X
SAE, ADE, SADE, USADE, procedure-related AE and device deficiencies ⁱ	—	X	X	X	X	X	X

Note 1: X = should be performed; O=optional (unless required based on other data); — = not required

Baseline assessments should be done within 30 days unless specified otherwise in the footnotes below. Eligibility for the study is determined per standard of care. Any additional study specific testing to verify inclusion/exclusion criteria must be done after the ICF is signed.

a: All follow-up dates will be calculated from the date of the (attempted) implant procedure. Subjects are considered enrolled in the study when the subject or the subject's legally authorized representative signs an ICF approved by the Independent Ethics Committee. Clinical follow-up is in-person at 14 days, 45 days, and 3 months. Follow-up at 12 months is in-person (preferred) or by telephone (unless an in-person assessment is required based on other data). Subjects who are enrolled but do not have a WATCHMAN FLX™ Pro LAA Closure Device implanted in the correct position will be followed for safety through 12 months after the initial attempted implant procedure by telephone or review of clinical files but will not undergo imaging assessments or evaluation of biochemical markers.

b: Risk factor assessments include HAS-BLED and CHA₂DS₂-VASC scores.

c: Either TEE or CT must be done within 14 days prior to the implant procedure (baseline assessment) following the core laboratory guidelines (see Section 12.3). CT at 14 days, 45 days, and 3 months are required for all subjects who have a WATCHMAN FLX™ Pro LAA Closure Device implanted in the correct position and should be performed per the core lab guidelines. TEE is required at 14 days, 45 days and optional at 3 months if there is no leak at 45 days, for all subjects who have a WATCHMAN FLX™ Pro LAA Closure Device implanted in the correct position and should be performed per the core lab guidelines. Results must be sent to the core laboratory for independent analysis (see Section 12.3).

[figure not shown]
d: Repeat TEE should be done at 12 months if the 3-month TEE assessment suggests a leak > 5mm or the 3-month CT assessment suggests a leak > 3mm; results must be sent to the core laboratory.

- e: MRI imaging assessments are optional. If MRI assessment is done, core laboratory guidelines should be followed. Results must be sent to the core laboratory for independent analysis (see Section 12.3).
- f: Labs include biochemical markers including measures of coagulation, platelet and endothelial activation and inflammation. At baseline, these labs should be obtained within 30 days prior to the implant procedure. Baseline serum creatinine is also required and should be obtained within 30 days prior to consent.
- g: Baseline neurological assessments should be done within 30 days prior to the implant procedure. For subjects diagnosed with a neurological event (e.g., stroke, TIA), mRS and NIHSS should be performed after the event. It is recommended that the subject be contacted regarding an mRS assessment at 90±14 days following any suspected stroke; the simplified mRS questionnaire may be used for this follow-up assessment and may be collected by telephone.

Note 2: If a subject has a stroke or other thromboembolic event, work-up should occur as per local standard of care. It is recommended that imaging be performed to screen for DRT. If performed, imaging results should be sent to the Core Laboratory.

- h: Procedural ICE data should be sent to the Core Laboratory.
- i: Safety events will be monitored and reported to Boston Scientific Corporation from the time of enrollment through 12-month follow-up. Please refer to Section 18.1 for a list of events to be adjudicated by the CEC through completion of a subject's participation in the study and **Table 25.2-1** for definitions of these events, which specify data required for CEC adjudication. Reporting of device deficiencies will follow applicable regional safety surveillance requirements.
- j: Required for subjects of childbearing potential and subject must have a negative pregnancy test after signing the ICF and prior to the implant procedure.

Abbreviations: ADE=adverse device effect; AE=adverse event; CEC=Clinical Events Committee; CHA₂DS₂-VASc=congestive heart failure, hypertension, age ≥75 years, diabetes mellitus, stroke/TIA, vascular disease, age 65–74 years, sex category; CT=computed tomography; DRT=device related thrombus; HAS-BLED=hypertension, abnormal renal/liver function, stroke, bleeding history or predisposition, labile INR, elderly, drugs/alcohol concomitantly; ICE=intracardiac echocardiography; ICF=Informed Consent Form; LAA=left atrial appendage; MRI=magnetic resonance imaging; mRS=modified Rankin Scale; NIHSS=National Institutes of Health Stroke Scale; SADE=serious adverse device effect; SAE=serious adverse event; TEE=transesophageal echocardiography; TIA=transient ischemic attack; USADE=unanticipated serious adverse device effect

* A subject is considered enrolled in the study when the subject or the subject's legally authorized representative signs an ICF approved by the IEC.

~ A subject of childbearing age must have a negative pregnancy test after signing the ICF to be enrolled in the study

^ Clinical follow-up is in-person at 14 days, 45 days, and 3 months and in-person (preferred) or by telephone at 12 months.

† Baseline CT or TEE must be done within 14 days prior to the index procedure.

‡ Repeat TEE should be done at 12 months if the 3-month TEE suggests a leak > 5mm or the 3-month CT assessment suggests a leak > 3mm.

Figure 10.1-1: WATCHMAN FLX Pro CT Study Event Schedule Summary Diagram

Up to 50 subjects will be enrolled. Dashed line indicates the assessment is optional unless required based on other data. Eligibility for the study is determined per standard of care. Any additional study specific testing to verify inclusion/exclusion criteria must be done after the Informed Consent Form is signed.

Please see **Table 10.1-1** for additional information.

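### Protocol 9.2 stops data collection after every withdrawal, whatever the reason, so deaths, strokes and bleeds after investigator discontinuation or loss to follow-up have no clear route into the 12-month safety data

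*Protocol*

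**What the plan says.** Protocol 9.2 defines withdrawal broadly: "Reasons for withdrawal include but are not limited to physician discretion, subject choice to withdraw consent, or death". Investigator decision and revoked consent are thus separate reasons under one heading. The consequences are the same for all: "Withdrawn subjects will not undergo any additional study follow-up, nor will they be replaced", and "No new data will be collected after subject withdrawal".

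The investigator may discontinue a subject who can no longer meet the study's requirements, "or if any of the study procedures are deemed potentially harmful to the subject". For these exits 9.2 adds: "If the withdrawal is due to investigator discretion, the investigator should follow-up with the subject per standard of care". Nothing is said about recording what that follow-up finds. If the exit is due to a device problem, the investigator asks for "permission to follow his/her status/condition outside of the clinical study".

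Protocol 9.3 defines loss to follow-up as a subject who "fails to be available for 2 consecutive scheduled visits without due cause and is unable to be contacted by study center staff". After calls and, if needed, a letter, "he or she will be considered to have withdrawn from the study with a primary reason of lost to follow-up", which brings the 9.2 stop into play.

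On analysis, SAP 7.1 uses Kaplan-Meier for time-to-event endpoints. SAP 9.3 and 9.4 base the 1-year binary rate on subjects who either had an event or have at least 335 days of follow-up.

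**The concern.** Neither an investigator-discontinued subject nor an unreachable one has revoked consent, yet both fall under a stop that suits only someone who has. After an investigator-discretion exit, the site may well learn of a later stroke or death through routine care, and 9.2 gives it no way to enter that event.

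The grounds for discontinuation can reflect failing health, and a subject may be unreachable because of a stroke or death. Leaving may therefore be associated with the 12-month outcomes, whereas Kaplan-Meier assumes that it is not. The binary rate treats leavers unevenly: event-free ones drop out of the denominator, while those with an earlier event stay in. No later analysis can recover outcomes that were never collected.

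At stake are the descriptive 12-month rates of death, stroke, systemic embolism and bleeding, and the part of the primary objective that relates tissue coverage to clinical events.

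**Working it through.** **The texts side by side.** The documents state no dropout rate and no figure to reproduce, so the first check is one of reading.

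- For the stop: 9.2 exempts no reason for exit. Its device-problem clause needs permission and lies outside the study. Section 9.5 deals with adverse events still open at exit and follows only device-related ones further. Note i to Table 10.1-1 ties committee adjudication to the subject's participation.
- Against it: note i also has safety events reported through the 12-month follow-up. Section 11.2.4 reports all events in device recipients. Table 18.4-1 requires SAE and committee-event reporting to the end of the study. Section 10.9 follows all enrolled subjects for 12 months.

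None of the texts in the second group mentions withdrawn subjects. Section 9.2 is the specific rule for them and probably prevails, but the protocol does not say so.

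**Effect of an exit on the SAP rate.** SAP 9.3 dates last follow-up from scheduled visits, discharge, the procedure or an adjudicated event. An on-window 3-month visit falls at day 90 + 30 = 120 at the latest. Since 120 < 335, an event-free subject who leaves before the 12-month visit drops out of the 1-year binary rate.

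**How much of the year could be lost.** Investigator discontinuation can occur at any time. For loss to follow-up, the second missed window must close first, so these are upper bounds that assume classification on that very day:

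- Day 14 and day 45 missed: window closes at 45 + 15 = 60; 365 − 60 = 305 days (84%).
- Day 45 and 3 months missed: window closes at 90 + 30 = 120; 365 − 120 = 245 days (67%).
- 3 and 12 months missed: window closes at 365 + 30 = 395; no prospective days lost.

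**Effect on a 12-month rate.** Inputs: N = 50 (Protocol 11.1.1); e = 3 observed events and k = 1, 3 or 5 event-free leavers, both assumed.

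- SAP binary rate = e/(N − k).
- Kaplan-Meier = e/N if all leavers are censored after the events, e/(N − k) if before them.
- Possible rate among all 50 = e/N to (e + k)/N, a width of k/N, or 1/50 = 2 points per leaver.

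| k | SAP binary | Kaplan-Meier | Possible rate |
|---|---|---|---|
| 1 | 3/49 = 6.1% | 6.0–6.1% | 6–8% |
| 3 | 3/47 = 6.4% | 6.0–6.4% | 6–12% |
| 5 | 3/45 = 6.7% | 6.0–6.7% | 6–16% |

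The upper ends require every leaver to have an event. Direction turns on very little: with k = 5, the reported 6.7% is too high if no leaver has an event (3/50 = 6.0%) and too low if one does (4/50 = 8.0%). The SAP still plans for 25 subjects; at that size each leaver is worth 1/25 = 4 points.

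**The case against.** The strongest reply is that reporting duties elsewhere reach beyond exit. A reader might infer from 9.2 alone that later events have no route at all into study data. The documents do not support that: Table 18.4-1, note i and 11.2.4 can each be read as still requiring the report. What stands is an unreconciled conflict in which the more specific rule points to non-collection.

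Second, a reader might infer that a subject who misses both the 3-month and 12-month visits has most of the year closed to file review. That does not follow. The stop begins only when the subject is classed as lost, 9.3 requires every effort at contact first and sets no deadline for classification, and nothing prevents the site from reading its own charts before then. Section 10.8 also asks for records of outside hospital stays that the site learns of. A death found during these efforts can be recorded as the reason for exit. The lost-to-follow-up case is therefore the smaller one.

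Third, few subjects need be discontinued. The power is permissive; a missed assessment is only a deviation (10.1), so a subject who stops imaging can stay in; and the 12-month visit may be by telephone. This limits frequency, which cannot be estimated, but does not remove the gap for those who are discontinued.

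Fourth, SAP 9.2 allows adjustment for missing outcomes, and 9.2 of the protocol captures exit reasons. Best- and worst-case bounds could be reported on that basis, but they would not replace the outcomes.

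Finally, materiality is low: the study is descriptive and safety is an additional measurement. The exact (Clopper-Pearson) 95% interval for 3/50, 1.3% to 16.5%, already contains every range in the table. That is conceded, although a sampling interval makes no allowance for selective non-ascertainment.

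**Conclusion.** The point holds as a cheap improvement. Section 9.2 applies one stop to exits that differ in consent status, and 9.3 extends it, so later safety events lack a clear route into the data. Investigator discontinuation is the main case.

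The size is unknown. Two points per event-free leaver is arithmetic at N = 50; the tabulated rates rest on assumed event and leaver counts. A reader might infer that the reported safety rates will be too low. The documents do not support a direction: dropping event-free leavers raises the binary rate, and unrecorded later events lower it. Informative loss is plausible from the grounds for discontinuation, not demonstrated.

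The primary imaging endpoint is unaffected, since the point concerns clinical events after exit. The consent pages were not available, so the form may already permit record review.

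**What to change.** In Protocol 9.2 and 9.3, limit the stop on new data to withdrawal of consent for data collection. Then, where consent and local law allow:

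- For investigator-discontinued subjects, continue to ascertain deaths and events for committee adjudication to 12 months, by the telephone or chart-review route that 10.8 already gives to subjects without an implant.
- For subjects lost to follow-up, do one clinical-file review at 12 months.
- Count that contact or review as the 12-month follow-up under SAP 9.3; otherwise it would not extend the last follow-up date of an event-free subject.
- Bring note i to Table 10.1-1 into line, so that adjudication covers these events.

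The cost is a protocol amendment and possibly a consent-form amendment, with ethics committee review (15.3) and possibly competent-authority review. Current subjects may need to re-consent; 7.1 refers to 25 already implanted. Beyond that there are occasional calls or chart reviews, with no new visits or procedures.
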